4.3 Study Endpoints

Safety Endpoints:

The number of patients with AEs, severity of AEs, number of patients with SAEs, clinically significant changes in laboratory values, and the number of patients who withdraw due to AEs.

Clinical Effects Endpoint(s):

- Change from baseline in the Total Functional Capacity (TFC), administered as part of the Unified Huntington's Disease Rating Scale (UHDRS)
- Change from baseline in the motor, cognitive, independence, and functional assessments administered as part of the UHDRS
- Change from baseline in the composite UHDRS (cUHDRS)
- Change from baseline in the Short Problem Behaviors Assessment (PBA-s)

Pharmacodynamic Endpoints:

- Change from baseline in the concentration of mHTT protein in CSF
- Changes from baseline MRI of the brain
- Change from baseline in exploratory biomarkers, including but not limited to neurofilament light (NFL)

PK Endpoints:

- PK parameters of WVE-120101 in plasma
- WVE-120101 and WVE-120101-related metabolite excretions in urine
- Concentration of WVE-120101 in CSF

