5.2 Exclusion Criteria

1. Clinically significant medical finding on the physical examination other than HD that, in the judgment of the Investigator, will make the patient unsuitable for participation in and/or completion of the study procedures.
 2. Received an investigational drug other than WVE-120101, including an investigational oligonucleotide, within the past 1 year or 5 half-lives of the drug, whichever is longer.
 3. Implantable CNS device that may interfere with ability to administer study drug via lumbar puncture or undergo MRI scan.
 4. Diagnostic and Statistical Manual of Mental Disorders 5th Edition (DSM-5) diagnosis at the Screening Visit of active alcohol, cannabinoid, or other substance use disorder (except nicotine).
 5. Positive for opioids (unprescribed), cocaine, amphetamines, methadone, barbiturates, methamphetamine, or phencyclidine at the Screening Visit.
 6. Pregnant (as determined by a serum pregnancy test) or breast feeding at the Screening Visit, or plans to become pregnant during the course of the study.
-

7. Clinically significant laboratory abnormality at Screening, including, but not limited to:
 - a. Alanine aminotransferase (ALT) or aspartate aminotransferase (AST) values at Screening or Baseline >3 times the upper limit of normal (ULN).
 - b. Renal insufficiency, defined as either serum creatinine >1.8 mg/dL or creatinine clearance <40 mL/min.
8. Clinically significant abnormality at Screening electrocardiogram (ECG), including but not limited to a confirmed QT interval corrected for heart rate (QTc) ≥ 450 msec for males or ≥ 470 msec for females.
9. Clinically significant cardiovascular, endocrine, hepatic, renal, pulmonary, gastrointestinal, neurologic, malignant, metabolic, psychiatric, or other condition that, in the opinion of the Investigator, precludes the patient's safe participation in the study or would interfere with the study assessments.
10. Bone, spine, bleeding, or other disorder that exposes the patient to risk of injury or unsuccessful lumbar puncture.
11. Inability to undergo brain MRI (with or without sedation).
12. In the opinion of the Investigator, deemed to be at significant risk for suicidal behavior

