8 METHODS OF ASSESSMENT AND ENDPOINTS

8.1 Safety Assessments

- Adverse events ([Section 9](#))
- Medical history and demographics
- Concomitant medications
- Physical examinations (including neurological and psychiatric)
- Vital signs
- Height and weight
- Electrocardiograms
- Clinical laboratory evaluations (including clinical chemistry, hematology, and urinalysis)
- Magnetic resonance imaging ([Section 8.5](#))
- Cerebrospinal fluid sample evaluations (cell count and total protein)
- Suicidality assessment
- Pregnancy testing

Any abnormal laboratory test results (hematology, clinical chemistry, or urine) or other safety assessments (e.g., vital sign measurements, C-SSRS) that are believed to be clinically significant in the medical and scientific judgment of the Investigator are to be recorded as AEs or SAEs.

8.1.1 *Medical History and Demographics*

Any changes in medical history since the completion of the parent study ([WVE-HDSNP1-001](#)) will be obtained at the Screening visit. Investigator assessment of medical history at Screening

will include information regarding any significant medical, surgical, psychiatric, and/or neurological conditions and treatments.

The current stage of HD, treatments received, and other details about this condition will be recorded.

Demographic data will include date of birth, sex, ethnic categorization, and race.

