10.4.2 Analysis of Safety Data

The summary of safety results will be presented by dose group. All safety analyses will be performed on the safety population using the following common rules:

- The OLE baseline value is defined generally as the last available value from WVE-HDSNP1-001 before first dose in WVE-HDSNP1-002.
- The repeat dosing baseline value is defined generally as the last available value before initiation of repeat dosing. Initiation of repeat dosing can occur in either WVE-HDSNP1-001 or WVE-HDSNP1-002.
- Adverse event observation periods are defined as follows:
 - Pre-OLE treatment AEs are AEs that developed or worsened between the date of signed informed consent for the OLE and the date of first dose of study drug in the OLE.
 - OLE on-treatment adverse events are AEs that developed or worsened from the first dose of study drug in the OLE to study completion/discontinuation. Summaries of TEAEs will include all OLE on-treatment AEs.
 - Repeat dosing on-treatment adverse events are AEs that developed or worsened from the first dose of repeat dosing to study completion/discontinuation. Initiation of repeat dosing can occur in either WVE-HDSNP1-001 or WVE-HDSNP1-002. Summaries of repeat dosing TEAEs will include all repeat dosing on-treatment AEs.
- For quantitative safety parameters based on central laboratory/reading measurement descriptive statistics will be used to summarize results and change from baseline values by visit and dose group.

Adverse Events

Treatment-emergent AEs, treatment-emergent SAEs, and TEAEs leading to treatment discontinuation will be summarized by dose group based on Medical Dictionary for Regulatory Activities (MedDRA) coding of verbatim terms reported by investigators.

Adverse event incidence tables will present, by system organ class (SOC) and preferred term, the number and percentage of patients experiencing an AE. Multiple occurrences of the same event will be counted once in the tables. The denominator for computation of percentages is the safety population within each dose group.

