Adverse event incidence tables will present, by SOC and preferred term, the number and percentage of patients experiencing an AE by severity and by relationship to treatment. In tabulating the severity of adverse events, the highest severity will be assigned to a subject with more than one occurrence of the same adverse event. The highest level of association will be reported in subjects with differing relationships for the same adverse event.

Similar tables will be generated summarizing repeat dosing TEAEs. Listings of all AEs, SAEs, deaths, and AEs leading to study discontinuation will be provided.

Clinical Laboratory Evaluations

Summary statistics of laboratory variables including CSF safety laboratory variables will be calculated for each visit or study assessment by dose group. Laboratory data will also be categorized as low, normal, or high based on the reference ranges of the central laboratory. Frequencies and percentages will be presented by dose group for the shifts in these categories from baseline to post-baseline assessment time points. A listing of clinically significant hematology and chemistry findings will be provided.

Other Safety Evaluations

Summary statistics of vital signs, ECG, and height and weight variables will be calculated for each visit or study assessment by dose group.

Columbia-Suicide Severity Rating Scale

Listings of patients who respond “yes” to item 4 or 5 on the C-SSRS at any point in the study will be provided.

Immunogenicity

Anti-drug antibody assay results to WVE-120101 will be described categorically. Summary statistics for anti-drug antibody titer results will be provided.

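### Section 10.4.2 classes laboratory values only as low, normal or high, so no planned output objectively counts patients by size of rise or shows concurrent ALT/AST and bilirubin elevation

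*Combined protocol and SAP*

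**What the plan says.** Section 4.3 names laboratory change among the safety endpoints: "number of patients with SAEs, clinically significant changes in laboratory values". It gives no numeric definition. Under section 3, safety and tolerability of long-term exposure is the primary objective.

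Section 10.4.2 plans these outputs that bear on laboratory values:

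- Visit summaries: "descriptive statistics will be used to summarize results and change from baseline values by visit and dose group". The statistics are not named.
- A three-level category: "Laboratory data will also be categorized as low, normal, or high based on the reference ranges of the central laboratory".
- A shift table: "Frequencies and percentages will be presented by dose group for the shifts in these categories from baseline to post-baseline assessment time points".
- A listing: "A listing of clinically significant hematology and chemistry findings will be provided". Table 3 in section 8.1.7 puts aPTT in a separate coagulation column, which the listing does not mention.
- AE tables by dose group, preferred term, severity and relationship, in which "Multiple occurrences of the same event will be counted once in the tables".

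A laboratory value reaches the AE tables by judgment. Section 8.1 says that abnormal results "believed to be clinically significant in the medical and scientific judgment of the Investigator are to be recorded as AEs or SAEs", and section 9.1 is to the same effect. Table 4 grades severity by symptoms and intervention, without laboratory cut-points. Numeric limits for ALT/AST (3 x ULN) and creatinine appear only as entry criteria, in exclusion 7 of section 5.2.

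**The concern.** A three-level category discards the size of a rise. All values above ULN are alike, and a patient who is already high at baseline shows no change of category however far the value climbs. Exclusion 7 limits such entry but does not rule it out.

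A safety report on a new exposure should be able to say how many patients at each dose had a large rise, including when the answer is few or none. The exposure here is new. At the data cutoff in section 1.4, experience was single doses up to 16 mg and multiple doses up to 4 mg. Section 4.1 now gives 16 mg or more every 4 weeks from Week 1 to Week 97, which is (97 - 1)/4 + 1 = 25 doses. The safety committee's review of this study ends when the parent study is complete (sections 4.4 and 13.1), so any later reading rests on the planned tables.

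**Working it through.** The plan states no figure to reproduce, and section 10.1 says that no sample size was calculated. The check is what each planned display can and cannot show.

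**Inputs.** From the documents: about 50 patients (section 5) and a possible 1:1 randomization to two doses (section 4.1). Assumed for illustration: 25 per group, or one group of 50; every unaffected patient at 0.6 x ULN, at baseline and later; four post-baseline visits.

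**1. Same displays, different patient counts.** In case A, one patient is at 6 x ULN at all four visits. In case B, four different patients are each at 6 x ULN at one visit. At every visit, in both cases, with n = 25:

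- mean = (24 x 0.6 + 6)/25 = 0.816
- SD = (6 - 0.6)/sqrt(25) = 1.08
- median 0.6, maximum 6
- mean change = 5.4/25 = 0.216
- one normal-to-high shift

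Patients above 5 x ULN, with exact 95% intervals:

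| Group size | Case A | Case B |
|---|---|---|
| 25 | 1/25 = 4% (0.1 to 20.4%) | 4/25 = 16% (4.5 to 36.1%) |
| 50 | 1/50 = 2% (0.05 to 10.7%) | 4/50 = 8% (2.2 to 19.2%) |

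With n = 50 the visit statistics again match in A and B: mean 0.708, SD 0.764, mean change 0.108.

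**2. What the shift table does settle.** The largest single-visit count of normal-to-high shifts is a lower bound, and the sum over visits an upper bound, on the number of patients with any rise above ULN from a normal baseline. In A and B the bounds are 1 and 1 + 1 + 1 + 1 = 4. If all these cells are empty, no patient with a normal baseline had a large rise at those visits. The table is objective, but silent on size.

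**3. Size of rise.** Case C is case B with each rise to 1.05 x ULN. The shift table equals that of B, yet no patient is above 3 x ULN. Only the visit statistics separate them: mean (14.4 + 1.05)/25 = 0.618 and SD 0.45/5 = 0.09, against 0.816 and 1.08.

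**4. High at baseline.** One patient goes from 2 to 20 x ULN with the other 24 at 0.6. The mean moves from (14.4 + 2)/25 = 0.656 to (14.4 + 20)/25 = 1.376, and the SD from 1.4/5 = 0.28 to 19.4/5 = 3.88. The visit summary shows it plainly. The shift table shows high to high, that is, no change.

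**5. Concurrent elevation.** ALT at 4 x ULN and bilirubin at 2.5 x ULN occur at one visit, either in one patient or in two different patients (other bilirubin values assumed at 0.5 x ULN). Bilirubin has mean (24 x 0.5 + 2.5)/25 = 0.58 and SD 2/5 = 0.40 either way, and the ALT table is unchanged too. Concurrent cases number 1 or 0, and tables by analyte cannot say which.

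**6. What counts could support.** For 1/25 against 4/25, Fisher's exact test gives p = 0.35. With no cases, the one-sided 95% upper bound on the true rate is 1 - 0.05^(1/25) = 11.3%, or 1 - 0.05^(1/50) = 5.8% in 50 patients. Such counts describe dose groups; they cannot formally compare them.

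**The case against.** The best reply is that the endpoint is analysed as written. It speaks of clinically significant changes, values judged so are recorded as AEs, and AE tables count each patient once by term, severity and dose group. The shift table is objective as well. With about 50 patients, a reader can count individuals from the listings, and a value of 6 x ULN would be absent only if the investigator judged it not clinically significant. The exact match of A and B also leans on equal baselines; with varied baselines the SD of change could differ. Nor do the documents point to a laboratory risk. Section 1.3 calls nonclinical potential for aPTT prolongation, liver and kidney toxicity minimal, and section 1.4 reports no meaningful laboratory trends.

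Most of this stands, and it limits the weight of the point. A reader might infer that the plan would miss a serious liver, kidney or coagulation case, or that it leaves the endpoint unanalysed. The documents support neither: AE recording, the listing and the visit summaries would probably bring such a case to light.

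What remains is narrower. Entry to the AE tables and the listing rests on judgment without a numeric definition, in an open-label study. A difference in SD between A and B would still not yield a patient count. Joint elevation is in no table, and aPTT falls outside the listing as worded.

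**Conclusion.** The point holds as an improvement that should be made, not as an error. No planned output objectively counts patients by size of rise, separates one patient with repeated large rises from several patients, or shows concurrent ALT/AST and bilirubin elevation, and the listing does not name coagulation. In the example, a fourfold difference in affected patients (4% against 16% in groups of 25, or 2% against 8% in 50) leaves the shift tables and visit statistics the same.

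The absence of such counts rests on the text of section 10.4.2 alone. The size rests on assumed laboratory values, equal baselines and assumed group sizes. No planned conclusion is invalidated, and the documents flag no specific laboratory signal.

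**What to change.** Keep the shift table and add to section 10.4.2 descriptive patient counts by dose group, from the central laboratory data already collected:

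- worst post-baseline ALT and AST in multiples of ULN (for example above 3, 5 and 10) and, for patients above ULN at baseline, in multiples of baseline;
- ALT or AST above 3 x ULN concurrent with bilirubin above a stated multiple of ULN (for example 2);
- worst post-baseline creatinine as a ratio to baseline;
- worst post-baseline aPTT in multiples of ULN.

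Only the ALT/AST limit of 3 x ULN has a source in the protocol, as an entry criterion. The other cut-points are proposals for the sponsor to settle. They are for reporting and set no treatment rule.

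Two rules are needed because patients change dose during the study (section 4.1) and section 10.4.2 defines two baselines. Attribute each worst value to the dose being received when it occurred, so that a patient who switches contributes one worst value per dose level, with the patients exposed to that dose as denominator. Use the OLE baseline for OLE tables and the repeat dosing baseline for integrated tables.

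Extend the listing of clinically significant findings to coagulation.

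The cost is analysis-plan wording and a few extra tables, mostly sparse. No new samples, visits or staff are needed.

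### No laboratory shift to the worst post-baseline value is specified, so patients who were ever out of range are not counted unless an investigator judged the value clinically significant

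*Combined protocol and SAP*

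**What the plan says.** Section 10.4.2 plans three kinds of laboratory table.

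- Summary statistics: "Summary statistics of laboratory variables including CSF safety laboratory variables will be calculated for each visit or study assessment by dose group".
- Change from baseline, for quantitative parameters measured or read centrally: "descriptive statistics will be used to summarize results and change from baseline values by visit and dose group".
- Category shifts: "Laboratory data will also be categorized as low, normal, or high based on the reference ranges of the central laboratory", and then "Frequencies and percentages will be presented by dose group for the shifts in these categories from baseline to post-baseline assessment time points".

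It also plans one patient-level output for laboratory data: "A listing of clinically significant hematology and chemistry findings will be provided".

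A second route runs through adverse events. Section 8.1 says abnormal results "believed to be clinically significant in the medical and scientific judgment of the Investigator are to be recorded as AEs or SAEs", and section 9.1 repeats the principle for events identified from study data. The incidence tables in 10.4.2 then give "the number and percentage of patients experiencing an AE. Multiple occurrences of the same event will be counted once in the tables".

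The safety endpoint in section 4.3 is "clinically significant changes in laboratory values". The primary objective in section 3 is safety and tolerability under long-term exposure.

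**The concern.** Whether a patient ever left the reference range is a question about the whole period, but the planned laboratory tables are organised by time point. A patient with one abnormal value in about two years is counted as abnormal in one column and normal in the rest. If different patients are affected at different visits, each column stays small and no table adds them up.

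The same section does state whole-period rules elsewhere. An adverse event is counted once per patient, the highest severity is assigned, and C-SSRS responses on two items are listed whenever they occur. Laboratory categories have no such rule, so a programmer following the text would build by-time-point shifts only.

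What is at stake is a descriptive count relevant to the primary objective. Section 1.3 lists aPTT prolongation, liver and kidney toxicity and pro-inflammatory effects as effects of the oligonucleotide class, while reporting minimal potential for them with this compound nonclinically. An occasional aPTT above range that nobody judged significant would appear only in scattered visit cells. Coagulation is a separate panel in Table 3 and is not named in the listing.

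**Working it through.** The plan states no laboratory abnormality rate or expected count, so there is no figure to reproduce. The check has two parts.

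**1. Which outputs count patients over the whole period?**

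| Output (section) | Unit | Whole-period patient count? |
|---|---|---|
| Summary statistics (10.4.2) | visit or assessment | No |
| Change from baseline (10.4.2) | visit | No |
| Low/normal/high shifts (10.4.2) | post-baseline time points | None specified |
| Listing of significant findings (10.4.2) | individual result | A listing, not a count; hematology and chemistry only |
| Adverse event tables (8.1, 9.1, 10.4.2) | patient, once per event | Yes, but only for values judged clinically significant |

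No row counts patients against the reference range over the whole period.

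**2. Can the count be recovered from the visit tables?**

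Inputs from the documents: about 50 patients (section 5), and dosing every 4 weeks from Week 1 to Week 97 (section 4.1), which is (97 − 1)/4 + 1 = 25 dosing visits, 24 of them after Week 1. Assessments every 12 weeks from Week 13 to Week 97 give (97 − 13)/12 + 1 = 8 visits, or 9 with Week 101. The laboratory row of Table 1 cannot be read reliably in the text available, so the number of laboratory visits k is an assumption. So are the abnormality rates.

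*Bounds.* If m of 50 patients are abnormal at each of k visits, with all 50 present, the number ever abnormal lies between m (always the same patients) and min(50, m × k) (always different patients). With independent visits it is 50 × [1 − (1 − m/50)^k].

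| m per visit | k | Minimum | Maximum | Independent visits |
|---|---|---|---|---|
| 1 | 8 | 1 | 8 | 7.5 |
| 2 | 8 | 2 | 16 | 13.9 |
| 1 | 24 | 1 | 24 | 19.2 |
| 2 | 24 | 2 | 48 | 31.2 |

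Identical visit tables therefore fit very different patient counts.

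*Within-patient correlation.* Let p be the chance of a new abnormal value per visit. With independent visits, the share ever abnormal is 1 − (1 − p)^k. For correlated visits, take a latent normal value with correlation ρ = 0.5 between any two visits and threshold z = Φ⁻¹(1 − p). The share is then 1 − ∫ Φ((z − √ρ·u)/√(1 − ρ))^k φ(u) du.

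| p per visit | k | Independent | ρ = 0.5 |
|---|---|---|---|
| 2% | 9 | 1 − 0.98^9 = 16.6% | 11.2% |
| 2% | 24 | 1 − 0.98^24 = 38.4% | 19.6% |
| 5% | 9 | 1 − 0.95^9 = 37.0% | 23.3% |

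If the same patients are always affected, the share stays at p. The gap between a visit table and the cumulative count thus runs from nothing to many-fold, and the planned tables cannot show where the trial falls.

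**The case against.** The strongest reply is that the laboratory endpoint concerns clinically significant changes, not any excursion outside a reference range. Such changes must be recorded as adverse events and are counted once per patient, and the hematology and chemistry ones are also listed. This stands. A reader might infer that the report will never show how many patients developed an abnormal value, or that the endpoint goes unanswered. The documents support neither inference: the gap is confined to out-of-range values that no investigator judged significant.

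The shift sentence also does not use the by-visit wording of its neighbours. Reading it as one shift per time point is natural but not literal, and an overall row is not ruled out. That too stands, but a row the plan does not ask for cannot be relied on.

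A reader might further infer that unscheduled repeat results are excluded. The plan does not say so; it gives no rule for them.

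Finally, the percentages rest on assumed rates, correlations and visit counts. They show that visit counts do not fix the cumulative count. They do not show that a safety signal would be missed.

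**Conclusion.** The point holds in limited form. Section 10.4.2 specifies no shift to a worst post-baseline value, so the number of patients who ever had an out-of-range laboratory result is not tabulated. The existing routes depend on investigator judgment or cover only part of the laboratory panel.

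No document figure gives the size. Under the stated assumptions, 2% per visit over 9 visits corresponds to 11% to 17% ever abnormal for latent correlations between 0.5 and 0, falling to 2% if it is always the same patients.

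The safety analysis is descriptive, so no test, error rate or sample size is affected. This is a worthwhile, inexpensive improvement to the tables and does not invalidate the safety analysis.

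**What to change.** Add to section 10.4.2, under Clinical Laboratory Evaluations:

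- For each centrally analysed laboratory parameter and dose group, one shift table from baseline to the lowest post-baseline value and one to the highest.
- Unscheduled central-laboratory results included.
- Denominator: patients with a baseline and at least one post-baseline value.
- A stated rule for the dose group to which the worst value belongs, for example the dose being received when it occurred. Section 4.1 lets patients change dose during the extension, so this cannot be left open.

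Keep the by-time-point tables. CSF safety samples and the platelet and prothrombin checks before lumbar puncture are tested locally (sections 8.1.7 and 8.1.8) and fall outside this change.

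The cost is a short addition to the text and two table shells, with no new data collection. The downside is in interpretation. Ever-abnormal percentages look less favourable than by-visit ones and rise with the number of visits even without a drug effect. There is no control group to set them against, so a footnote should say this and give the number of assessments per patient.
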